There are a limited number of clinical trials addressing maternal oxygen administration for fetal distress in labor. In 1995, Thorp et al conducted a randomized trial of oxygen versus room air in the second stage of labor, and found no benefit to oxygen exposure and in fact discovered that the oxygen group had a lower umbilical artery pH. This difference was theorized to be a result of fetoplacental vasoconstriction as a result of prolonged oxygen exposure. Similarly, Nesterenko et al performed a trial of laboring women randomized to oxygen or room air and found that more infants in the oxygen group required delivery room resuscitation. Excess oxygen exposure in this setting has also been linked with increased free radical activity. In a 2002 trial by Khaw et al,

women were randomized to oxygen or room air during cesarean delivery. There was no difference in umbilical artery pH between groups, however the oxygen exposed group had increased free radical activity in cord blood samples. Studies such as these have prompted questioning of both the safety and the efficacy of oxygen for Category II FHT and highlight the urgent need for further investigation, particularly given its wide-spread use.

The primary objective of this study is to evaluate whether oxygen for intrauterine fetal resuscitation of Category II FHT affects fetal metabolic acid-base status as determined by umbilical cord lactate values. Secondary objectives include analysis of additional cord gas parameters used to predict neonatal wellbeing, changes to FHT patterns, and cord blood and maternal MDA as a marker of free radical activity. We hypothesize that room air exposure for Category II FHT in labor is no different from maternal oxygen administration with regard to fetal acid-base status.

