## **Data Collection**

The patient's primary nurse will perform real-time documentation of oxygen initiation, any disruption in intervention, administration of amnioinfusion and additional resuscitation techniques performed (number of times patient is repositioned, total intravenous fluids, discontinuation of oxytocin). Study staff will collect data from medical records on:

- 1) Antepartum history:
  - a. Demographic data: Maternal age, race
  - b. Obstetric history: parity, prior cesarean, gestational age at delivery
  - c. Medical history: BMI at initial prenatal visit, diabetes, chronic hypertension, severe anemia (Hemoglobin <7), tobacco use, illicit drug use
  - d. Prenatal course: diagnosis of hypertensive disorders, gestational diabetes, abruption, intrauterine growth restriction, oligohydramnios
- 2) Intrapartum data:
  - a. Indication for admission/induction
  - b. Oxytocin (duration, total received dose)
  - c. Analgesia
  - d. Duration of labor (first and second stage)
  - e. Diagnosis of chorioamnionitis
  - f. Mode of delivery
  - g. Indication for cesarean
  - h. Electronic fetal monitoring
- 3) Neonatal course:
  - a. APGARs
  - b. Neonatal weight

- c. Admission to special care nursery (SCN) or neonatal intensive care unit (NICU)
- d. Duration of admission to SCN or NICU
- e. Diagnosis of any of the following: hypoxic ischemic encephalopathy, respiratory distress syndrome, oxygen requirement, requirement of hypothermia therapy, seizures, sepsis or suspected sepsis, neonatal death

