## **Statistical Analysis**

Intention-to-treat (primary analysis) and per protocol analyses will be performed. Chi-squared and Fisher's exact tests will be used to compare categorical variables as appropriate. Continuous variables will initially be assessed for distribution pattern via the Kolmogorov-Smirnov test. Normally distributed variables will be compared using Student's t-tests and non-normally distributed variables will be analyzed with the Mann-Whitney U test. These analyses will be supplemented by multivariable logistic regressions to adjust for confounders.

Tests with  $p < 0.05$  will be considered statistically significant. Analyses will be performed using Stata (Stata Corp., College Station, TX).

For the primary outcome of lactate, 95% confidence intervals (CI) will be calculated for the mean cord lactate levels in each group. Comparison of the 95% CI in each group will then determine non-inferiority or inferiority.

Additional interaction analyses for the primary outcome will be performed for the following subgroups:

- 1) Presence of chronic medical conditions (hypertensive disorder, diabetes)

- a. Patients with hypertensive disorders (chronic hypertension, gestational hypertension, preeclampsia)
- b. Patients with diabetes mellitus (gestational diabetes, T1DM, T2DM)
- 2) Recurrent late decelerations pre intervention
- 3) Recurrent variable decelerations pre intervention
- 4) Prolonged deceleration pre intervention
- 5) Fetal tachycardia pre intervention
- 6) Fetuses with intrauterine growth restriction
- 7) Chorioamnionitis
- 8) Within oxygen group: Duration of oxygen exposure
  - a. <50% of total duration of active labor (onset of active labor to delivery)
  - b. >50% of total duration of active labor (onset of active labor to delivery)

Odds ratios and 95% CI will be calculated for the secondary outcome of persistent Category II FHT. Kaplan-Meir analyses will be performed for fetal monitoring analyses.

For the outcome of maternal and cord blood MDA, a fetal MDA will be calculated by subtracting umbilical artery MDA from maternal MDA for each sample. The calculated mean fetal MDA and maternal MDA values will then be compared between groups using either Student t test or Mann Whitney U test.

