### **Sample size analysis**

A review of previously collected data from our institution of 5182 term singleton pregnancies revealed a mean cord lactate of  $3.5 \pm 1.6$  mmol/L in women with Category II FHT within 30 minutes of delivery. All of these deliveries were managed using our current protocol of routine oxygen administration for Category II FHT. Given the normal mean lactate seen in our population of patients with Category II FHT, a noninferiority approach was selected to test our hypothesis that room air is not inferior to oxygen administration in treating Category II FHT. A total sample size of 98 patients will be needed to detect a non-inferiority margin of 30% with 90% power, using a one-sided two-sample t-test (alpha 0.025). To accommodate a 15% drop out/cross over rate, a total of 114 patients will be needed. We plan on performing an initial compliance run-in of 6 patients making the total enrollment 120 patients. Data analysis will only be performed on the 114 patients enrolled after the initial 6 patients enrolled/randomized in the compliance run-in/pilot. Previous studies have shown an increased risk for neonatal morbidity with cord lactate cut-offs ranging from 3.2-6.0. The margin of noninferiority was

therefore set at a lactate cut-off of 4.5, above which there is a clear association with neonatal morbidity.

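### Oxygen exposure in the within-arm duration analysis is cut at 50% of active labor without a stated reason; a slope on the derivable percentage would be more precise if the relation is graded

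*Combined protocol and SAP*

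**What the plan says.** The Statistical Analysis section announces: "Additional interaction analyses for the primary outcome will be performed for the following subgroups". The eighth entry is "Within oxygen group: Duration of oxygen exposure", with two classes: "<50% of total duration of active labor (onset of active labor to delivery") and ">50% of total duration of active labor (onset of active labor to delivery"). The section gives no reason for 50%, plans no analysis with exposure on its full scale, and names no specific test for this item. The only regression it names is logistic, which does not give a slope of lactate on exposure.

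Under Data Collection the primary nurse performs "real-time documentation of oxygen initiation, any disruption in intervention", and study staff collect "Duration of labor (first and second stage"). The time of onset of active labor, where the plan's percentage begins, is not listed as an item of its own.

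The question has a basis in the protocol. Background/Significance reports a lower umbilical artery pH with oxygen in an earlier second-stage trial, a difference "theorized to be a result of fetoplacental vasoconstriction as a result of prolonged oxygen exposure".

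**The concern.** A quantity that can be derived on a fine scale is reduced to two classes. A woman exposed for 10% of active labor counts the same as one at 49%, and one at 51% the same as one at 100%. Exactly 50% belongs to neither class, though few women are likely to fall there.

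The analysis uses one arm only, so it starts with little information. If the relation is graded, the two-class comparison gives a less precise answer than the data allow and cannot show the shape of the relation. A null result could then be read as evidence that duration does not matter, on a question the Background raises as a possible harm. At stake is the reading of one exploratory analysis.

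**Working it through.** **Arm size.** The plan gives no power for item 8, so the arm size comes from the primary calculation in the Sample size analysis: lactate 3.5 ± 1.6 mmol/L, margin 30%, 90% power, "using a one-sided two-sample t-test (alpha 0.025").

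- Margin: 0.30 × 3.5 = 1.05 mmol/L.
- n per arm = 2 × [1.6 × (1.960 + 1.282) / 1.05]² = 48.8, so 49 per arm and 98 in total, as stated.
- The plan inflates this to 114. With 1:1 allocation that is 114 / 2 = 57 in the oxygen arm, or 49 after planned loss.

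**Assumptions that are not in the documents.** Correlation r between exposure and lactate of 0.2 to 0.4; a linear relation; exposure distributed uniformly or normally; the cut dividing the arm between 50/50 and 80/20; a two-sided test at 0.05 (the plan gives p < 0.05 without sidedness); and a two-group t-test for the cut version.

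**Information kept by the cut.** Under linearity, cutting multiplies r by a factor a. With p the share of women on one side of the cut:

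- normal exposure: a = φ(c) / √(p(1−p)), where φ(c) is the standard normal density at the cut;
- uniform exposure: a = √(3p(1−p)).

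The information kept is about a².

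| Split | a², normal | a², uniform |
|---|---|---|
| 50/50 | 0.798² = 0.64 | 0.866² = 0.75 |
| 80/20 | 0.700² = 0.49 | 0.693² = 0.48 |

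These shares do not depend on r. For 57 women with uniform exposure, 0.75 × 57 ≈ 43 and 0.48 × 57 ≈ 27 women's worth of information remain.

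**Power.** Noncentral t with n − 2 degrees of freedom and noncentrality r√n / √(1 − r²); for the cut, r is replaced by a × r. Example with n = 57, r = 0.3, uniform exposure:

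- continuous: 0.3 × 7.550 / 0.954 = 2.37, power 64.5%;
- cut at 50/50: a × r = 0.260, noncentrality 2.03, power 51.4%;
- cut at 80/20: a × r = 0.208, noncentrality 1.60, power 35.1%.

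| n | r | Exposure, split | Continuous | Cut | Loss (points) |
|---|---|---|---|---|---|
| 49 | 0.2 | uniform, 50/50 | 28.8% | 22.6% | 6 |
| 49 | 0.3 | normal, 50/50 | 57.8% | 39.4% | 18 |
| 49 | 0.4 | uniform, 80/20 | 84.9% | 50.7% | 34 |
| 57 | 0.3 | normal, 50/50 | 64.5% | 44.8% | 20 |
| 57 | 0.4 | uniform, 80/20 | 89.9% | 57.1% | 33 |

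The first and third rows are the smallest and largest losses over the assumed grid.

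**Outside the grid.**

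- At r = 0.1 the loss is about 1 to 4 points. For n = 57, continuous power is 11.6%, against 9.9% for the cut (uniform, 50/50) or 8.1% (uniform, 80/20).
- For r = 0.2 to 0.5 and splits out to 90/10, the loss runs from about 4 to 55 points.
- If lactate instead steps at 50%, the ordering reverses. With n = 57, a correlation of 0.3 between class and lactate, and uniform exposure, the cut has 64.5% power, against 51% for the slope at 50/50 and 35% at 80/20.

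**The case against.** The strongest objection is that the power loss is not a property of this plan. Correlation, split, distribution and linearity are all assumed, and under a step at 50% the cut wins. This stands. A reader might infer that the cut costs 6 to 34 points outright; the documents do not support that, and the range holds only under the stated assumptions. The theory of prolonged exposure quoted in the Background concerns pH in another trial and fits a threshold as well as a trend. Still, no document proposes a threshold at 50%, so the plan gives no ground for staking the analysis on one.

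A second objection is that scale is not the main weakness of item 8. Under the Strategy section women are randomized when Category II tracing appears in active labor, and per-protocol oxygen covers at least 90% of what remains. The exposed fraction therefore depends largely on when the tracing changed and how long labor lasted. A slope estimates the same confounded association more precisely and does not make it causal. This also stands, and it is why the result needs a non-randomized label.

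Third, a reader might infer that exposure is already recorded as a continuous quantity. It is not: initiation and disruptions are documented, duration must be derived, and onset of active labor is not listed separately. But the 50% classes cannot be assigned without the same percentage, so the slope asks for nothing extra.

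Finally, the plan names no test for item 8 and allows the Mann-Whitney test for non-normal variables, which was not modelled here. The power figures would shift somewhat. The loss of exposure detail would remain.

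**Conclusion.** The point holds as a cheap improvement to an exploratory analysis. Item 8 cuts a derivable exposure at an unexplained 50% with nothing continuous beside it. If the relation is roughly linear, the cut keeps about 64-75% of the information at an even split and about 48-49% at 80/20, whatever the correlation. For 49 to 57 women and assumed correlations of 0.2 to 0.4, this is about 6 to 34 points of power; at weaker correlations it is small, and under a step at 50% it turns into a gain. A reader should not infer that the main conclusion is affected: item 8 lies within one arm and enters neither the non-inferiority comparison nor the sample size.

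**What to change.** Make item 8 a linear regression of umbilical arterial lactate on the percentage of active labor exposed to oxygen, entered as a continuous variable, and report the slope with its 95% CI. Name the percentage as the single exposure measure: it is the plan's own, and minutes would be a different exposure that also tracks labor length. Keep the 50% grouping as a descriptive table with one class made inclusive (for example ≥50%). Label the result exploratory and non-randomized, because the exposed fraction depends on when Category II tracing appeared and on labor length.

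The cost is a sentence or two of analysis-plan text, with no new patients and no data beyond what the two classes already require. The downside is that the slope assumes approximate linearity, which 49 to 57 women can check only weakly.

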**Secondary Aim #1: Characterize the effect of oxygen administration on fetal heart tracing patterns**

*Hypothesis: Oxygen administration will be associated with a rate of persistent Category II FHT that is not different from those exposed to room air.*

Oxygen is typically administered in response to FHT interpretation. Hence, evaluating the effect of oxygen on subsequent FHT is pivotal to labor management. The primary outcome will be resolution of Category II FHT. We will also investigate the effect of oxygen administration on mode of delivery, particularly cesarean delivery for non-reassuring fetal status.

**Secondary Aim #2: Evaluate the safety of oxygen administration by measuring reactive oxygen species (ROS) in maternal and neonatal blood.**

*Hypothesis: Oxygen administration will be associated with increased oxidative stress in maternal and neonatal cord blood as represented by malondialdehyde (MDA).*

Over-oxygenation can result in free radical or ROS formation that have detrimental downstream effects. The presence of reactive oxygen species results in degradation of lipids in the cell membrane and resultant formation of malondialdehyde (MDA), which has been studied as a surrogate for oxidative stress.

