## **Specific Aim 2: Characterize the effect of oxygen administration on fetal heart tracing patterns**

In clinical practice, oxygen is administered to patients with Category II FHT in order to resuscitate potential fetal hypooxygenation that manifests as heart rate decelerations. Evidence thus far shows that Category II FHT are associated with a wide spectrum of neonatal outcomes and therefore do not uniformly reflect fetal acid-base status. Hence, evaluating the effect of oxygen on subsequent FHT categorization is pivotal to labor management. The outcome that will be investigated is rate of persistent Category II FHT after intervention. We will also evaluate the types and frequency of deceleration patterns present both pre and post intervention. We hypothesize that oxygen administration for Category II FHT will be associated with a rate of persistent Category II FHT that is not different from those exposed to room air.

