Consent will be obtained at time of admission to Labor & Delivery. Randomization to either the oxygen group or room air group will be performed when the patient is in active labor (defined as regular contractions and  $\geq 6$  cm cervical dilation) and develops Category II FHT necessitating intrauterine resuscitation as determined by the care provider team (Figure 3). This will be performed via a computer-generated randomization sequence in a 1:1 ratio. Patients randomized to the oxygen group will receive the above stated current management of oxygen via nonrebreather face mask at 10L/min and “per-protocol” defined as receiving the mask for at least 90% of the remaining duration of labor including during cesarean delivery. Patients randomized to the room air group will not receive oxygen for Category II FHT unless otherwise required for maternal indications. Alternative and/or additional intrauterine resuscitation techniques for both groups (i.e. fluid bolus, maternal repositioning, and discontinuation of oxytocin) will be left to

the discretion of the medical team. The initial 6 patients consented and randomized will be part of a compliance run-in with the same protocol as above.

[figure not shown]

Figure 3: Flow diagram for randomization and treatment groups  
 L&D: Labor and Delivery FHT: fetal heart tracing

Specific Aim 1: Determine the effect of maternal oxygen administration for Category II FHT on neonatal cord gas parameters

After delivery of the infant, a segment of the umbilical cord will be removed with immediate collection of umbilical artery and vein samples by trained providers. These samples will be sent to the hospital laboratory for routine cord gas measurements as is universally practiced on our Labor and Delivery unit.

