#### Specific Aim 2: Characterize the effect of oxygen administration on fetal heart tracing patterns

The patient's primary nurse will document the time at which intervention is initiated. A blinded investigator will then retrospectively assess FHT categorization and deceleration patterns both pre and post intervention.

Specific Aim 3: Evaluate the safety of oxygen administration by measuring ROS in maternal and neonatal blood

We will be measuring serum MDA in both cord and maternal blood as a marker of oxidative stress. MDA is a byproduct of lipid peroxidation, which occurs as a result of oxidative stress. Measurement of Thiobarbituric Acid Reactive Substances (TBARS) is a commonly used assay

for quantifying MDA This assay is performed by fluorometrically measuring the MDA-TBA complex formed in plasma or serum by the reaction of MDA and TBA.

Upon delivery of the infant, an additional sample of umbilical artery blood will be collected for this analysis. An optional sample of maternal blood will also be drawn within 60 minutes of delivery. Both blood samples will be centrifuged to collect plasma which will then be stored at -80°C until the TBARS assay is performed.

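### Kaplan-Meier is named for the fetal monitoring analyses with no rule for delivery before resolution; the usual censoring at delivery would overstate the proportion of Category II tracings that resolve

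*Combined protocol and SAP*

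**What the plan says.** The Statistical Analysis section gives the method in one sentence: "Kaplan-Meir analyses will be performed for fetal monitoring analyses". It names no event, time origin, rule for delivery, horizon or test between arms. The sentence before it plans a separate analysis: "Odds ratios and 95% CI will be calculated for the secondary outcome of persistent Category II FHT". That one has no time window either. No method for competing events is named anywhere in the document.

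The outcome is worded in two ways. Secondary Aim #1 in Specific Aims has: "The primary outcome will be resolution of Category II FHT". Specific Aim 2 in Background/Significance has: "The outcome that will be investigated is rate of persistent Category II FHT after intervention". Secondary Aim #1 also covers mode of delivery, "particularly cesarean delivery for non-reassuring fetal status".

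The Strategy section defines per-protocol oxygen as "receiving the mask for at least 90% of the remaining duration of labor including during cesarean delivery", so the intervention period runs to delivery. Under Specific Aim 2 of that section, the patient's "primary nurse will document the time at which intervention is initiated", and a blinded investigator later reads the tracing before and after that time.

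**The concern.** Time from the start of intervention to resolution is the natural thing to plot with Kaplan-Meier here. Some patients will deliver while the tracing is still Category II. The default is to censor them at delivery, which treats them as if they would have gone on to resolve at the same rate as patients still in labor.

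There are two difficulties. After delivery the tracing can no longer resolve, so delivery is a competing event and not ordinary loss to follow-up. Delivery may also be prompted by the tracing: the protocol itself lists cesarean for non-reassuring status under the same aim. Patients censored early may therefore be those least likely to resolve.

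What is at stake is the reading of a secondary aim. Its hypothesis is that persistence of Category II does not differ between oxygen and room air, so a curve that hid a difference would appear to support the hypothesis.

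**Working it through.** The plan states no figure for this analysis, so there is nothing of its own to reproduce. Its sample size rests on lactate alone. The documents give no resolution or delivery rates, so **every hazard below is an assumption**.

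**Formulas.** Let r be the hourly hazard of resolution and d the hourly hazard of delivery, both constant, and t the time in hours.

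- One minus Kaplan-Meier (1−KM), delivery censored: 1 − exp(−r·t)
- Proportion who resolve before delivery (cumulative incidence): r/(r+d) × [1 − exp(−(r+d)·t)]

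**1. Overstatement, t = 2, r = 0.5.**

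- 1−KM = 1 − exp(−1) = 0.632, whatever d is.
- d = 0.5: cumulative incidence = 0.5 × [1 − exp(−2)] = 0.432.
- d = 1.0: cumulative incidence = 0.333 × [1 − exp(−3)] = 0.317.

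The curve reads 63% where 43% or 32% have resolved. Over r from 0.2 to 0.5, d from 0.15 to 1.0 and t from 1 to 4, the excess runs from 1 to 53 percentage points. It is zero if nobody delivers before the horizon.

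**2. Delivery driven by the tracing, t = 4.** Take two severity types in equal shares: r = 0.6 with d = 0.2, and r = 0.1 with d = 0.6.

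- 1−KM (simulated): 0.727.
- Cumulative incidence: 0.5 × (0.6/0.8) × [1 − exp(−3.2)] + 0.5 × (0.1/0.7) × [1 − exp(−2.8)] = 0.427.
- Resolution if delivery never intervened: 0.5 × [1 − exp(−2.4)] + 0.5 × [1 − exp(−0.4)] = 0.619.

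The curve is too high for both targets.

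**3. Comparison of arms, t = 4.** Take r = 0.3 in both arms, with d = 0.3 in one and 0.9 in the other.

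- 1−KM = 1 − exp(−1.2) = 0.699 in both arms.
- Cumulative incidence = 0.5 × [1 − exp(−2.4)] = 0.455, against 0.25 × [1 − exp(−4.8)] = 0.248.
- In 4,000 simulated trials with 57 per arm (114/2), the log-rank test rejected in about 6% and a comparison of proportions resolved in about 65%.

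The order of the arms can also reverse. With two equal severity types again, let one arm have r = 0.6 and 0.2 with d = 0.2 and 0.3, and the other r = 0.6 and 0.05 with d = 0.2 and 1.2. Simulation then gives 1−KM of 0.747 against 0.824, but cumulative incidence of 0.533 against 0.378.

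**4. Does the rule for delivery matter?** Keep patients who deliver unresolved in the risk set up to the horizon, with no other censoring. The Kaplan-Meier product then telescopes to (n − events)/n, so 1−KM equals events/n, the cumulative incidence. Under the hazards in step 1 this returns 43% and 32%. The problem therefore lies in how delivery is handled, which the plan leaves open.

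**The case against.** The strongest reply is that the plan does not say what this point fears. It names neither time to resolution as the event nor censoring at delivery. A reader might infer that the plan commits to a biased curve, or that no form of Kaplan-Meier could be right here. The documents do not support the first, and step 4 disproves the second. What stands is that censoring at delivery is the usual default and nothing in the plan rules it out.

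A second reply is that Kaplan-Meier is not the only analysis. The odds ratio for persistent Category II addresses the hypothesis directly, and cesarean for non-reassuring status is already an outcome. If unresolved at delivery counts as persistent, the odds ratio could reveal a difference that the curve hides. This has force, but the plan states neither that rule nor a time window, so the safeguard is partial.

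A third reply is that when resolution hazards are equal, as in step 3, oxygen has no effect on how fast tracings resolve while labor continues. With independent delivery, the equal curves answer that question correctly. Cumulative incidence also counts quick uncomplicated deliveries against resolution. This is right, and it is why the cause-specific comparison should be reported as well. It does not make 1−KM a proportion of patients who resolved.

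**Conclusion.** The concern holds in conditional form. If the event is resolution and delivery is censored, 1−KM overstates the proportion who resolve whenever deliveries precede resolution. The direction is certain under those two conditions. The size cannot be computed from the documents; 63% against 43% at 2 hours is an illustration with assumed hazards.

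A masked or distorted difference between arms requires more: delivery rates, or their dependence on the tracing, must differ by arm. That is possible but not shown. A reader might infer that the plan is tilted toward finding no difference on this aim. The documents do not support that, because they show no such imbalance and also plan the odds ratio.

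This is a secondary outcome. The primary lactate result and the sample size are unaffected. The gap is still worth closing, because a standard remedy exists at almost no cost.

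**What to change.** In the Statistical Analysis section:

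- Define the event (what counts as resolution), the time origin (the nurse-documented start of intervention, in both arms) and the horizon.
- Replace the Kaplan-Meier curve for resolution with the cumulative incidence of resolution, treating delivery without resolution as a competing event (Aalen-Johansen estimate, with a risk difference and 95% CI at a fixed time).
- Beside it, report the cause-specific comparison for resolution and the cumulative incidence of delivery for non-reassuring status.
- State that unresolved at delivery counts as persistent in the odds ratio.

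The cost is a few sentences and slightly more analysis with standard Stata commands. Data Collection already lists electronic fetal monitoring, labor duration, mode of delivery and the indication for cesarean. It does not list the indication for operative vaginal delivery, which would have to be added if those deliveries are to count as non-reassuring. The downsides are a less favourable-looking resolution curve and a cumulative incidence that also reflects the speed of uncomplicated delivery, which is why the cause-specific result is shown with it.
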